### **Secondary Outcomes:**

PrEP Uptake - ever accepted a PrEP prescription from the MCH clinic

PrEP adherence by DBS - any tenofovir-DP detected, tenofovir-DP detected above specific levels (to be defined; analyses are ongoing to better characterize optimal levels in women in general and pregnant women specifically)

Partner HIV status known by end of follow up- by maternal-report when available. Because partners in both trial arms can access HIV testing at the clinic, this data will be captured from maternal MCH cards as available

Infant outcomes – preterm birth, birthweight, 9-month growth (weight, height)

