## **5. STATISTICAL ANALYSES AND DESCRIPTION OF MAIN TABLES**

**AIM 1a:** The proportion of all women enrolled in the study who use PrEP (proportion of women exposed to PrEP) will be compared between trial arms using GEE with a binomial link.

**AIM 1b:** The proportion with 'appropriate' use will be compared between arms using GEE with a binomial link. PrEP adherence will be measured among women on PrEP using DBS TFV drug levels. All women receiving PrEP will have 3-monthly DBS samples available. For each trial arm (10 clinic-cluster) a random subset of 220 DBS will be assessed. TFV drug levels will be compared by trial arm using GEE with a Gaussian link. PrEP duration will be computed for each woman based on self-report and pharmacy records and average duration compared between arms using GEE with a Gaussian link. Reported and confirmed partner with HIV status, proportions of partner HIV positive, unknown and HIV negative status, and reported and confirmed partner ART use will be compared between arms using GEE with a binomial link.

Infant outcomes: mean birthweight and serial weight-for-age z-scores (WAZ), height-for-age z-scores (HAZ), and weight-for-height z-scores (WHZ) will be compared between trial arms using GEE with a Gaussian link. A separate analysis will assess birth and infant outcomes by PrEP exposure in the combined arms.

**AIMS 2-4** will be conducted after the primary analysis and will not be reviewed by the EAC.

---

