**Table 2. Primary and secondary endpoints**

	N (%) or incidence/100 py			RR (95% CI), p-value
	All subjects	Trial arm		
		Universal	Targeted	
Primary outcomes				
HIV incidence				
Initiated on PrEP				
Secondary endpoints				
'Appropriately' on PrEP (based on risk score)				
Partner known HIV status by end of follow-up				
Partner on ART if HIV infected				
TFV-DP levels (median on random sample)				

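### Neither DBS adherence outcome in SAP section 2 (TFV-DP detected; TFV-DP above a cut-off) has an analysis: section 5 compares only mean levels, and the results shell shows a median beside a risk ratio

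*SAP*

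**What the plan says.** Three parts of the SAP describe the adherence outcome in three forms.

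- **Definition (SAP section 2, Secondary Outcomes).** Adherence by DBS is "any tenofovir-DP detected, tenofovir-DP detected above specific levels (to be defined; analyses are ongoing". The first part is a yes/no outcome. The second is a yes/no outcome at each cut-off, once the cut-offs are set.
- **Analysis (SAP section 5, Aim 1b).** In each arm, "a random subset of 220 DBS will be assessed". The one comparison given is "TFV drug levels will be compared by trial arm using GEE with a Gaussian link". The same paragraph treats another yes/no outcome differently: "The proportion with 'appropriate' use will be compared between arms using GEE with a binomial link". Partner status and partner ART are also given a binomial GEE.
- **Reporting (SAP section 9, shell Table 2, primary and secondary endpoints).** The adherence row is "TFV-DP levels (median on random sample". The summary header is "N (%) or incidence/100 py", and the only effect column is "RR (95% CI), p-value".

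The protocol does not settle the form. Its Table 7 names the TFV-DP and FTC results from 440 specimens without choosing a summary. Its laboratory methods section (Component 1, part f) adds a fourth form: TFV-DP bands that approximate tablets per week, with boundaries at 350, 700 and 1,250 fmol/punch.

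**The concern.** Better adherence in the targeted arm is a stated hypothesis under protocol Aim 1b. An analyst who follows section 5 to the letter will test a difference in mean concentration and will test neither outcome that section 2 lists. The p-value printed in the shell would then belong to neither the defined endpoint nor the median beside it.

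Two practical consequences follow. First, detection, threshold, mean, median and banded versions are all available, and the SAP's randomization text describes the study as unblinded. The version reported could be chosen after arm-level results are known. Second, a mean needs a numerical value for samples with no detectable drug, and the SAP gives no rule for one.

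**Working it through.** **Plan's own figure.** The SAP assays 220 DBS per arm, and 2 × 220 = 440 agrees with the protocol's total. The number of assays is consistent; the gap is in what is done with them.

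**Definition against analysis.**

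| Quantity | Section 2 outcome? | Section 5 comparison? | In the shell? |
|---|---|---|---|
| Any TFV-DP detected (yes/no) | Yes | None | No |
| TFV-DP above a level (yes/no) | Yes, cut-offs open | None | No |
| Mean TFV level | No | Gaussian GEE | No |
| Median TFV-DP | No | None | Yes, beside an RR column |

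A Gaussian GEE names a distribution rather than a link. With the identity link presumed, it estimates a difference in means, not a risk ratio and not a median.

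**Can the quantities diverge?** The documents give no detection rates, spread of levels or ICC for this outcome, so everything below is assumed. Levels are zero when undetected and lognormal when detected, with detection probability p, median m among detected and log-SD s.

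- Mean = p·m·exp(s²/2)
- Variance = p·m²·exp(2s²) − mean²

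*Case 1, constructed so that the means cancel*

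- Arm A (p = 0.50, m = 1,000, s = 0.60): mean = 0.50 × 1,000 × exp(0.18) = 599; variance = 0.50 × 1,000² × exp(0.72) − 599² ≈ 668,900; SD ≈ 818.
- Arm B (p = 0.75, m = 650, s = 0.65): mean = 0.75 × 650 × exp(0.211) = 602; variance = 0.75 × 650² × exp(0.845) − 602² ≈ 375,000; SD ≈ 612.
- Means, 220 per arm, unclustered: SE = √[(668,900 + 375,000)/220] ≈ 69. The difference of about 4 is 0.05 SE, so a two-sided 5% test rejects about 5% of the time, which is its error rate.
- Detection, 50% vs 75%: power = Φ{[0.25 − 1.96·√(2 × 0.625 × 0.375/n)] / √[(0.25 + 0.1875)/n]}. With n = 220 this exceeds 99%. With 22 samples per clinic and ICC 0.05, the design effect is 1 + 21 × 0.05 = 2.05, n = 220/2.05 = 107, and power is about 97%.
- Share at or above 700 fmol/punch (one of the protocol's band boundaries): about 36% in A and 34% in B. A threshold outcome set there would also show almost nothing.

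*Case 2, same levels among detected women (m = 800, s = 0.60 in both arms), detection 50% vs 75%*

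- Means 479 and 718, difference 239. SE = √[(428,100 + 470,100)/220] ≈ 63.9. Ratio 3.75, so power ≈ Φ(3.75 − 1.96) ≈ 96% unclustered.
- With the same design effect of 2.05: 3.75/√2.05 = 2.62, so power ≈ Φ(0.66) ≈ 74%. Detection has about 97% on that footing.

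*Case 3, same detection (60%) in both arms, medians 600 vs 800, s = 0.60*

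- Means 431 and 575. SE = √[(258,000 + 458,700)/220] ≈ 57.1. Ratio 2.52, so power is about 71% unclustered. The test of detection rejects at its 5% error rate.

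No single summary stands in for the others. Case 1 shows a detection difference with equal means, and Case 3 shows a difference in means with equal detection. Repeated samples from one woman are ignored throughout.

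**The case against.** The strongest case on the other side has five parts.

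- **A comparison of levels is legitimate.** This stands. With 220 samples per arm, skewness alone does not invalidate a comparison of means, and Case 3 shows that it can find a difference in intensity of use that detection cannot. The fault is that it is the only comparison specified and is not the listed outcome.
- **A reader might infer that the planned test will hide a real adherence difference.** The documents do not support that. The spike at undetectable and the long right tail are assumptions, not facts in the protocol or SAP. Case 1 needs detection to rise by half while levels among detected fall by 35%, with a slightly different spread in each arm. In Case 2 the Gaussian test works well.
- **The cut-offs are openly still to be set, and the wording could fit graded categories.** This is fair for the second outcome. It does not cover any detection, which needs no cut-off and still has no analysis.
- **The risk-ratio column is a shared header in an empty shell.** This also stands. A reader might infer that a ratio of medians would be reported as a risk ratio, but nothing in the SAP says so. Alone this would be a presentational point; here it is a further sign that no single target was chosen.
- **Adherence is a secondary outcome.** Correct. The HIV incidence and PrEP-use comparisons are not touched.

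**Conclusion.** The point holds as a mismatch between endpoint and analysis: SAP section 2 lists detection and level above a cut-off, section 5 analyses neither, and the shell summary matches neither section. This rests on the text alone and needs no distributional assumption.

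The size of the consequence is not fixed by the documents. Under the assumed distributions, power to see a change in detection from 50% to 75% through the Gaussian comparison ranges from the 5% error rate (Case 1) to about 96% unclustered (Case 2). A direct test of detection keeps over 99% unclustered and about 97% at ICC 0.05. These cases show that the quantities can separate; they do not predict that they will. The matter is worth correcting because adherence is a named hypothesis and the correction is cheap, but it does not threaten the primary results.

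**What to change.** 1. **SAP section 5.** Compare between arms (a) the proportion of sampled specimens with any TFV-DP detected and (b) the proportion above a cut-off fixed before arm-level data are seen. Use GEE with binomial family and log link, robust standard errors and clustering on clinic, and report risk ratios. This follows the SAP's approach to its other yes/no outcomes and fills the shell's effect column.
2. **Levels as supportive.** Keep the comparison of TFV levels, with a written rule for undetected values and the link named, or analyse the bands in the protocol's laboratory methods section as ordered categories.
3. **Shell Table 2.** Replace the adherence row with n (%) detected and n (%) above the cut-off, each with its risk ratio. Show median (IQR) as descriptive only, outside the effect column.

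The cost is wording in the SAP and shell, plus slightly more analysis of a secondary outcome. No specimens are added to the 440 already planned.

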### **Randomization scheme text for a randomized, unblinded study**

The facility-level cluster randomization will be conducted using a restricted randomization approach based on new antenatal care clinic (ANC) volume, and county. County will be used as a proxy for HIV prevalence.

We will select 20 clinics from Western Kenya. Ten clinics will be randomized to universal PrEP and ten to targeted PrEP (Table 2). To ensure balance between study arms in terms of key site characteristics, sites will be categorized on HIV prevalence and ANC volume, and restricted randomization will be used for site (cluster) allocation to intervention and control arms (67). Specifically, all possible randomizations that evenly distribute sites on these two specified factors (HIV prevalence, ANC volume) into 2 study arms will be generated, and one combination will be selected using a random number generator. Randomization and allocation will be performed by [name], who has no knowledge of sites other than the variables included in the restricted randomization process.

In order to build excitement for the study among study staff and facility representatives, we aim to conduct the final randomization activities as part of the study training. Prior to the training, each facility was ranked by county and ANC volume and assigned to one of six groups. The ANC volume and county for each group are summarized in Table 1.

Table 1: Summary of facility group assignments for PrIMA randomization activities			
Group	County	Number of Facilities	Mean ANC Volume (SD)
1	Homa Bay	2	173 (60.8)
2	Homa Bay	4	59.8 (1.3)
3	Homa Bay	4	53.8 (3.3)
4	Siaya	2	140 (26.9)
5	Siaya	4	54.8 (6.4)
6	Siaya	4	38 (5.5)

One representative from each facility will be identified to represent their facility during the randomization event. Representatives from facilities in each group will be asked to select a ball from a bag during the PrIMA training. The bag will contain one ball per facility, and half of the balls will be blue (universal arm) and half of the balls will be orange (targeted arm). The final facility randomization will be determined by what color ping pong ball the facility representative selects. Facility group assignments are including in Table 2.

### **6. INTERIM ANALYSIS PLAN**

Prior to RCT initiation, we will convene an external advisory panel (EAP) to review study aims and protocol. At annual EAP meetings enrollment, retention, and pooled outcomes will be reviewed. Because of the short RCT timeline and potentially imbalanced follow-up time between sites, we do not plan to conduct an interim comparison of outcomes.

**8. PROPOSED TIMELINE**

	2016	2017		2018		2019		2020		2021
Activity	June-Dec	Jan-Jun	Jul-Dec	Jan-Jun	Jul-Dec	Jan-Jun	Jul-Dec	Jan-Jun	Jul-Dec	Jan-Mar
Study Protocol Developed										
Consent forms developed										
Kiswahili translated consent										
CRFs development										
IRB/ERC Applications										
SOPs developed										
SOP and CRF Training										
IDI Guides developed										
FGD guides developed										
Facility Eligibility Criteria data collected										
Facilities Randomized										
Data Collection- Aims 1 and 2										
Data collection- Aim 3										
Data analysis										
Manuscript writing										
Final Close-Out										
Dissemination of results										

9. APPENDIX: SHELL TABLES AND FIGURES

Figure 1. Flow diagram of cumulative enrollment for Universal and Targeted Arms

**Table 1. Distribution of demographic and clinical characteristics of women by randomization arm**

	N (%) or Median (IQR)		
	Overall	Project arm	
		Universal	Targeted
Demographic characteristics			
Age (years)			
Median age			
<25			
25-35			
≥35			
Marital status			
Currently married			
Divorced/separated			
Cohabiting			
Never married			
Widow			
Education (years)			
Regular employment			
People per room			
Risk assessment characteristics			
No. of lifetime sexual partners			
HIV status of sexual partner(s)			
Positive			
Negative			
Unknown			
No male partner			
RPR reactive			
Pregnancy history			
Gestational age at enrollment (weeks)			
Primigravida			
Previous abortion/miscarriages			
Previous premature birth (<37 weeks)			
Psychosocial scales			
Perceived risk of HIV scale score			
HIV treatment adherence self-efficacy score			
CESD-10 score			
HITS score			

**Table 2. Primary and secondary endpoints**

	N (%) or incidence/100 py			RR (95% CI), p-value
	All subjects	Trial arm		
		Universal	Targeted	
Primary outcomes				
HIV incidence				
Initiated on PrEP				
Secondary endpoints				
'Appropriately' on PrEP (based on risk score)				
Partner known HIV status by end of follow-up				
Partner on ART if HIV infected				
TFV-DP levels (median on random sample)				

**Supplementary Table 1. Distribution of demographic characteristics of women screened and enrolled in the study**

	N (%) or Median (IQR)			
	Project arm			
	Universal		Targeted	
	Screened (n=)	Enrolled (n=)	Screened (n=)	Enrolled (n=)
Demographic characteristics				
Age (years)				
Median				
<10				
21-34				
≥35				
Gestational age (weeks)				
Plan to receive postnatal care services at this facility				

**Table 2. Partner characteristics and self-test results for targeted arm**

	N (%) or Median (IQR)			p-value
	Overall	Self-test		
		Accepted (n=)	Declined (n=)	
Participant Characteristics				
Participants enrolled in targeted arm				
Self-Tests Distributed to Participants				
Self-tests distributed by participants to sexual partners				
Sexual partners who refused a self-test				
Partner characteristics				
Partner HIV status				
Positive				
Negative				
Unknown				
Living together with partner				
Yes				
No				
Married to partner				
Yes				
No				
Partner self-test results				
Positive				
Negative				
Unkown				
No response				

How does the participant know the results of the self test?				
Partner took test with participant present				
Partner told participant the results				
Partner showed participant the test results				
Other
